155 orals agents [40, 41, 43-48]. It is still not known whether these favorable effects extent to  
156 the more challenging group of patients with type 2 diabetes who have a baseline HbA1c  
157 >10%. Liraglutide reduces blood glucose by several mechanisms independent of insulin  
158 secretion and its superior effect on HbA1c and weight loss was found to be largely  
159 independent of diabetes duration and baseline HbA1c [39]. Treatment with GLP-1  
160 agonists has also been associated with low secondary failure rates, durable and sustained  
161 long term blood glucose control, and durability of the initial weight loss [39, 42, 49].

162

163 **Given all these distinct properties of GLP-1 agonists and simplicity of use, we**  
164 **propose they could represent a viable alternative to intensive insulinization in**  
165 **patients with very uncontrolled (HbA1c >10%) type 2 diabetes.**

166

167 The aim of this study is to compare a GLP-1 plus basal insulin treatment regimen to a  
168 basal-bolus treatment regimen in patients with very uncontrolled (HbA1c>10%) type 2  
169 diabetes. We will compare the two regimens with respect to efficacy in improving  
170 glycemic control, rate of hypoglycemia, change in weight, effect on patient quality of  
171 life, treatment burden, physician time, as well as healthcare related cost. We hypothesize  
172 that the two treatment regimens will have equal effectiveness, while the GLP-1 based  
173 regimen will be superior with respect to all other variables.

174

175 We chose to focus on a specific patient population which is generally considered to be  
176 most challenging to manage, use up greater healthcare resources, have higher potential for  
177 morbidity, and have traditionally been excluded from most clinical trials. Therefore this  
178 study will fill in an existing knowledge gap and provide high level evidence for future  
179 diabetes treatment guidelines pertaining to this patient population. We will obtain  
180 information not only in regards to the effectiveness of the treatment, but also safety and  
181 impact on healthcare cost beyond the cost of the drug.

182

183 Our findings will have great impact on the way we treat this – unfortunately – significant  
184 segment of the diabetic population, with huge potential benefits beyond just glycemic  
185 control, including quality of life, other metabolic co-morbidities, healthcare cost, etc.  

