## 211 **Specific aims:**

- 212 1. Compare the two treatment regimens with respect to a disease and patient-  
213 relevant composite outcome of effectiveness (HbA1c <7%) and safety (no  
214 hypoglycemia and no weight gain);
- 215 2. Compare the two treatment regimens with respect to treatment burden (number of  
216 daily shots, amount of glucose self-monitoring, need for treatment titration);
- 217 3. Compare the two treatment regimens with respect to quality of life [as measured  
218 by a disease specific (DQOL) questionnaire and general health (SF-36)  
219 questionnaire];

220 4. Compare the two treatment regimens with respect to all healthcare related costs:  
221 actual cost of the pharmacologic agents, glucose monitoring supplies, all other  
222 pharmacologic (non-study related) and non-pharmacologic healthcare related  
223 costs (outpatient and inpatient, diabetes related and non-diabetes related). We will  
224 also compare actual physician time spent during office visits and non-visit related  
225 care of these patients. While no actual dollar amount can be attached to this  
226 (phone visits and longer office visits required by the need for extra patient  
227 education are not customarily reimbursable) time commitment is of great  
228 relevance to our physicians who care for these very complex patients.  
229

230 **Primary outcome:**

231 Change in HbA1c from randomization to 26 weeks of therapy.  
232

233 **Secondary outcomes:**

- 234 1. The main secondary outcome is a less traditional but very patient-centric and  
235 clinically meaningful composite outcome of HbA1c <7% AND no documented  
236 hypoglycemia (capillary glucose level <56 mg/dl) AND no significant weight  
237 gain (<3% body weight) during the 6-mo study follow-up;
- 238 2. % reaching target HbA1c of <7% at end of study;
- 239 3. 7-point glucose profile results;
- 240 4. % patients reaching pre-specified “treatment failure” outcome;
- 241 5. Change in weight from baseline (both absolute weight lost and percent of body  
242 weight);
- 243 6. % patients with weight loss >5% of body weight;
- 244 7. Number of hypoglycemic episodes defined as mild (symptoms of hypoglycemia  
245 confirmed by a CBG reading of <70 mg/dl), moderate (any CBG reading <56  
246 mg/dl), severe (need for help to recover regardless of CBG reading);
- 247 8. Number of patients experiencing any hypoglycemic episodes;
- 248 9. DQOL questionnaire score;
- 249 10. SF-36 questionnaire score;

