### 735 **Statistical Analysis Plan**

736 All statistical analyses will be performed by the study statistician ([name]), who  
737 has extensive experience in clinical trials analysis.

738 Primary analysis: The primary analysis will be intention-to-treat (ITT) which will include  
739 all randomized participants who receive at least one dose of a study medication. The  
740 non-inferiority of liraglutide treatment strategy compared to standard basal-bolus insulin  
741 regimen will be assessed using a 95% confidence interval for the between treatment  
742 group net difference (month 6 minus month 0) in HbA1c at 6 months. This 95%  
743 confidence interval will be derived from the differences of least square means estimated  
744 from a mixed model repeated measures analysis. Non-inferiority of liraglutide treatment  
745 will be concluded if the upper limit of the 95% confidence interval is less than the non-  
746 inferiority margin of 0.4%.

747

748 Secondary analyses: We will also perform a per-protocol analysis comparing HbA1c  
749 response because, in non-inferiority hypothesis testing, the ITT analysis may be biased  
750 toward the null hypothesis. The per-protocol population is defined as the population who  
751 continued the assigned intervention as randomized for the duration of the study period.  
752 Secondary outcomes include the composite endpoint of HbA1c<7% with no  
753 hypoglycemia and no significant weight gain, a binary variable, which will be compared  
754 between the randomized study groups with a logistic regression model. The odds ratio  
755 and corresponding 95% confidence intervals will be reported. From healthcare related  
756 cost data, cost-effectiveness ratios will be summarized as point estimates with 95%  
757 confidence intervals, accounting for the skewness in the distribution of the ratio[50].  
758 Sensitivity cost analyses will be performed to further assess variables such as treatment  
759 failure and quality of life weights. Multiple logistic regression models will be constructed  
760 to evaluate any association of baseline covariates on treatment efficacy. Binary  
761 secondary endpoints will also be assessed with logistic regression models. Group  
762 comparisons and changes from baseline over time (study visits) of continuous secondary  
763 outcome variables will be analysed with mixed model repeated analysis. The logrank test  

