764 will be used to compare the pre-specified “treatment failure” end-point between groups.  
765 Safety endpoints and hypoglycemic and other adverse events will summarize in detail  
766 with descriptive statistics. The analysis of safety data will be performed for the ITT  
767 population.

768 Model assumptions regarding normality and covariance structure will be carefully  
769 assessed. Nonparametric tests or data transformations will be used if necessary to meet  
770 assumptions. Statistical analysis will be performed with SAS software (SAS Institute,  
771 Cary NC), particularly Proc Mixed for linear models with both fixed and random effects.

772 A two-sided alpha <5% will be considered significant for all analyses.

773

774 **Interim Analysis**

775 No interim analysis is planned.

776

777 **DATA HANDLING AND RECORD KEEPING:**

778 All data will be collected in strict compliance with the University's HIPPA rules.

779 Research records (source documents) will be kept in a double-locked filing system in a  
780 secure locked room. Collected data will be stored in an electronic study database will be  
781 encrypted and password protected and saved on the University's secure network. Only  
782 study personnel will have access to these records.

783

784 The institutional review board (IRB) governing this study may inspect the medical  
785 records of any patient involved in this study at any time.

786

787 Laboratory specimens will be collected under standard of care protocol at Parkland  
788 hospital laboratory and handled in accordance with the hospital policy.

789

790 The study blind will be maintained by the designated statistician and only broken by  
791 request from a treating physician in case of a medical emergency.

792

793 **ETHICS:**

794 Ethical Considerations:

795 1. Exclusion of non-English speakers- while translators are available during working  
796 hours, the investigators are worried that no translator will be available to assure  
797 safety measures at all times.

798 2. Compliance with Insulin Regimen- At times patients are not compliant with  
799 complicated insulin regimens and providers often continue to uptitrate insulin  
800 dosage when patients remain above HbA1c goal. If patient compliance improves  
801 once enrolled in the study, there is a higher risk of hypoglycemia. Every effort  
802 will be made at all visits to determine exactly what amount of insulin the patient  

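### The plan hypothesises a lower hypoglycaemia rate but names no model that estimates or compares the episode rate between arms (secondary outcome 7)

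*Combined protocol and SAP*

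**What the plan says.** All references are to the combined protocol and SAP.

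- **Background and Significance, closing paragraphs.** The two regimens are to be compared on "glycemic control, rate of hypoglycemia, change in weight, effect on patient quality of" life and other variables. Equal effectiveness is expected, and the GLP-1 "regimen will be superior with respect to all other variables".
- **Secondary outcomes.** Item 1, the main secondary outcome, is the "clinically meaningful composite outcome of HbA1c <7% AND no documented" hypoglycaemia (glucose below 56 mg/dl) and no significant weight gain. Item 7 is a count by severity: "Number of hypoglycemic episodes defined as mild (symptoms of hypoglycemia" with a confirming reading below 70 mg/dl), then moderate and severe. Item 8 is "Number of patients experiencing any hypoglycemic episodes".
- **Statistical Analysis Plan.** The composite is compared by logistic regression, with an odds ratio and 95% confidence interval. Binary "secondary endpoints will also be assessed with logistic regression models. Group" comparisons of continuous secondary outcomes use a repeated-measures mixed model. On hypoglycaemia in its own right, the plan says: "Safety endpoints and hypoglycemic and other adverse events will summarize in detail", by descriptive statistics. Nonparametric tests or transformations are allowed if model assumptions fail.
- **Assessments for Safety.** Hypoglycaemia is listed first. Patients record each episode with its date and time. Mild episodes are defined here as symptomatic or asymptomatic.
- **Subject Replacement.** Drop-out of 12% is expected, and withdrawn patients are not replaced.

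**The concern.** Less hypoglycaemia is one of the reasons the protocol gives for preferring the liraglutide regimen, and the hypothesis is worded as a rate. A rate needs a count and an exposure time. Outcome 7 supplies the count, but the plan does not say how the arms will be compared on it and does not mention exposure. Two problems follow.

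1. The trial could end without a rate ratio and confidence interval for a hypothesis it states. Raw totals are not comparable between patients followed for different lengths of time.
2. Several analyses of the same diaries would be open: total counts, ranks, any/none, or by severity. Patients and treating doctors know the assignment (Blinding), so naming one analysis in advance protects against a choice made after seeing the data.

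**Working it through.** **1. The plan's own figure.** The only power statement that involves hypoglycaemia is for the composite: at least 80% for 25% versus 5%, two-sided 0.05. With n per arm and pooled proportion 0.15, power = Φ[(0.20 − 1.96·s0)/s1], where s0 = √(2·0.15·0.85/n) and s1 = √((0.25·0.75 + 0.05·0.95)/n).
- n = 50: s0 = 0.0714, s1 = 0.0686, giving Φ(0.876) = 0.809.
- n = 44: 0.756 by the same formula, or 0.804 by exact enumeration of the uncorrected chi-square test.

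The stated figure reproduces at 50 per arm, or at 44 with the exact uncorrected chi-square. It says nothing about the episode rate.

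**2. Which rule covers which outcome.**

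| Outcome | Rule in the plan | Gives an episode rate? |
|---|---|---|
| Composite (item 1) | Logistic regression, explicit | No; a difference can come from HbA1c or weight |
| Any episode (item 8) | Logistic regression, as a binary endpoint | No; one episode and twenty count alike |
| Number of episodes (item 7) | Descriptive; arguably mixed model or nonparametric fallback | No; no follow-up time in any of these |

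**3. What a rate model would add.** The documents give no episode rate or dispersion, so these are assumptions: 50 per arm (100 randomised 1:1), gamma-Poisson counts, and 12% of patients with partial follow-up.

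Analytic check with full follow-up: the variance of the log rate ratio is (1/μ₁ + 1/μ₂ + 2k)/n, with k the dispersion, and power is Φ(ln 2/SE − 1.96).
- 4 vs 2, k = 1.0: (0.25 + 0.50 + 2)/50 = 0.055; SE 0.2345; Φ(0.996) = 0.84.
- 4 vs 2, k = 1.5: (0.25 + 0.50 + 3)/50 = 0.075; SE 0.2739; Φ(0.571) = 0.72.
- 6 vs 3, k = 1.5: (0.167 + 0.333 + 3)/50 = 0.070; SE 0.2646; Φ(0.660) = 0.745.

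For any/none, the chance of at least one episode is 1 − (1 + kμ)^(−1/k). For 4 vs 2 and k = 1.0 that is 0.80 vs 0.667. The step 1 formula, with these proportions, gives power 0.32.

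Simulated power with 12% partial follow-up:

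| Control vs liraglutide, k | Negative binomial | t-test, raw counts | Rank test | Any/none |
|---|---|---|---|---|
| 4 vs 2, 1.0 | 0.83 | 0.81 | 0.70 | 0.34 |
| 4 vs 2, 1.5 | 0.72 | 0.68 | 0.53 | 0.26 |

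For 6 vs 3 and k = 1.5, negative binomial power is 0.73 against 0.21 for any/none. With rarer episodes the gap to any/none narrows: at 1 vs 0.3 and k = 1.0 it is 0.93 against 0.79. Type I error of the negative binomial test was about 5 to 6% in the null simulations.

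**4. Differences, first and second table row.** Against any/none: 0.83 − 0.34 = 0.49 and 0.72 − 0.26 = 0.46. Against the rank test: 0.13 and 0.19. Against the t-test: 0.02 and 0.04.

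**The case against.** A reader might infer that hypoglycaemia is only described, and that the trial cannot test any claim about it. The documents do not support that. The composite contains a hypoglycaemia component and is tested and powered. Item 8 is a binary secondary endpoint, so the logistic regression rule covers it. The descriptive sentence does not say that nothing else will be done, and it can be read as safety reporting alongside those tests.

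A reader might also infer that no valid test of counts is possible under the plan. If item 7 is treated as a continuous secondary outcome, the mixed model applies, with transformation or rank methods as fallback. In simulation with equal drop-out in both arms, a t-test on total counts, used as a simple stand-in for that route, kept its size (type I error 0.054 and 0.041). It lost only a few points of power. Nor is hypoglycaemia alone the primary or main secondary outcome; the count is item 7 of 25.

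These points stand, and they limit the finding to the episode rate. They do not supply what is missing. It is unclear whether item 7 falls under the continuous rule at all. If it does, the result is a difference in mean counts or ranks, not a rate ratio adjusted for follow-up. The large power gap applies only against any/none. It depends on assumed rates and shrinks when episodes are rare.

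**Conclusion.** The point holds as a specification gap confined to secondary outcome 7. The plan hypothesises superiority on a rate, collects the counts, and names no method that estimates the rate or accounts for time at risk. No stated figure is wrong, and outcome 8 and the composite remain testable as planned.

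The power gain depends on what would otherwise be done. Under the assumed rates it is nearly 50 points over any/none, 13 to 19 over a rank test, and only 2 to 4 over a t-test on raw counts. The case therefore rests mainly on having a pre-specified, exposure-adjusted rate ratio for a stated hypothesis. All power figures depend on assumed means, dispersion and drop-out pattern, because the documents give no hypoglycaemia rate.

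This is a free improvement worth making.

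**What to change.** 1. **Reconcile the definition first.** The Secondary outcomes list requires symptoms for a mild episode, whereas Assessments for Safety includes asymptomatic ones. State which definition the count uses.
2. **Add one analysis for outcome 7.** Use negative binomial regression of the number of episodes per patient, with log follow-up time as offset. Include treatment, insulin use at screening and BMI stratum (cut-off 37 kg/m²) as terms. Report the rate ratio with 95% confidence interval for all episodes and for moderate-or-worse episodes. If severe episodes are sparse, summarise them descriptively rather than fit a separate model.
3. **Keep the rest.** Retain the descriptive tables and the logistic analyses, and say explicitly that outcome 8 is analysed by logistic regression, so that the descriptive sentence is not read as replacing it.

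The cost is a short addition to the Statistical Analysis Plan and one standard model in SAS, which the plan already uses. Dated diary entries and an assessment at every visit are already planned, so no new data and no change in sample size are needed.

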 457 meals taken daily. Meal-time insulin titration, if needed, can be either patient driven (see  
 458 table below) or physician-directed during the scheduled follow-up visits (phone or in  
 459 person), as well as any unscheduled patient-initiated visits (if applicable).

460

461 Novolog patient self-titration table:

Glucose prior to lunch	Change in breakfast insulin dose	Glucose prior to dinner	Change in lunch insulin dose	Glucose prior to bedtime	Change in dinner insulin dose
<54	-2 units	<54	-2 units	<54	-2 units
55-69	-1 unit	55-69	-1 unit	55-69	-1 unit
70-120	No change	70-120	No change	70-130	No change
121-160	+1 unit	121-160	+1 unit	131-180	+1 unit

>160	+2 units	>160	+2 units	>180	+2 units
------	----------	------	----------	------	----------

462

463 **Rescue therapy:**

464 Should any patients randomized to liraglutide treatment experience persistent  
465 hyperglycemia (defined as a confirmed Hb1c>10%) at the 3-mo visit (visit 5), meal-time  
466 insulin aspart will be initiated per the same protocol as above. This is a pre-specified  
467 “treatment failure” end-point. Following initiation of rescue therapy patients will  
468 continue all scheduled visits and procedures through the end of the trial.

469

470 Should any patients randomized to the “standard of care” group experience persistent  
471 hyperglycemia (defined as a confirmed HbA1c >10%) at the 3-mo visit (visit 5),  
472 treatment and insulin titration will continue as scheduled. This is also a pre-specified  
473 “treatment failure” end-point.

474

475 A graphical review of the visit procedures and timing is presented below:

Visit	1	2	3	4	5	6
Time	3-7	0	2 weeks	1	3	6
Type	Office	Office	Phone	Office	Office	Office
Consent	x					
I&E criteria	x					
Randomization criteria		x				
Randomization		x				
Physical exam	x			x	x	x
Height	x					
Vitals (weight, BP, pulse)	x	x		x	x	x
Dietary counseling	x	x	x	x	x	x
Lifestyle counseling	x	x	x	x	x	x
7-point glucose		x				x
Labs (HbA1c, lipids, CMP, Hb)	x				x	x
Dispense trial drug		x		x	x	
Hypoglycemia assessment	X	X	X	x	x	x
Frequency of glucose monitoring				x	x	x
Titrate insulin		x	x	x	x	
Liraglutide titration (if applicable)			x			
Insulin dose assessment		x	x	x	x	x
Compliance assessment				x	x	x
# daily injections				x	x	x
QoL questionnaires (DQOL and SF36)		x				x
AE and SAE assessment		x	x	x	x	x
Pregnancy test (if needed)	x	x		x	x	x
Physician time assessment		x	x	x	x	x

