## 574 **RISKS ASSOCIATED WITH THE PARTICIPATION IN THE STUDY:**

### 575 Risks of Liraglutide:

576

577 Very common (reported by more than 10 percent of the patients):

578

- - Gastrointestinal adverse events are the most common side effect of liraglutide and reported in up to 41% of patients. Nausea is seen in approximately 13% of patients treated with liraglutide and is usually developed in the first 2 weeks. It tends to be mild, dose-related and decline over time. In some patients the nausea can be more severe and be associated with vomiting which is usually transient and self-resolving.

583

584

585

Common (reported by 5-10 percent of the patients)

586

- Low blood sugar (hypoglycemia) - - The risk of having hypoglycemia with liraglutide is higher if taking it with another medicine that can cause hypoglycemia, such as a sulfonylurea or insulin. In some people, the blood glucose may get so low that they need another person to help them. The dose of your sulfonylurea medicine or insulin may need to be lowered while using liraglutide.
- Headache and upper respiratory tract infections have been reported in 7-9% of patients treated with liraglutide. A similar percentage of patients developed headaches with placebo or comparator drug.

594

595

596

Uncommon side effects (reported by 1-5 percent of the patients):

597

- Injection site reactions (e.g., injection site rash, erythema) were reported in approximately 2% of liraglutide treated patients in the five clinical trials of at least 26 weeks duration. Less than 0.2% of liraglutide-treated patients discontinued due to injection site reactions.

600

601

602

Very rare side effects (affects less than 1 percent of patients)

603

- Acute pancreatitis (inflammation of the pancreas) - there have been few reported event of acute pancreatitis presenting with persistent severe abdominal pain (usually accompanied by vomiting). Patients experiencing the above symptoms should contact the study doctor who will decide on whether they should discontinue the trial medication and /or require additional diagnostic procedures.
- Rarely, a severe form of allergic reaction (anaphylactic reaction) with additional symptoms such as breathing problems, swelling of throat and face, fast heart beat

609

610 etc. has been reported with marketed use of Liraglutide. Patients experiencing  
611 these symptoms should seek immediate medical help and inform the trial doctor  
612 as soon as possible.

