803 is taking and the overall compliance.

804

805 Informed Consent:

806 Informed consent will be obtained during the first face-to-face contact. Once a  
807 prospective subject is identified, we will explain the study details and preliminary  
808 eligibility is accessed either through phone or face-to-face interview. If the prospective  
809 volunteer remains interested in the study and fulfils preliminary eligibility criteria,  
810 baseline studies are scheduled. Only study personnel listed on the consent will be  
811 permitted to obtain consent. The subject will be provided informed consent and it will be  
812 signed and witnessed. The consent form will discuss the procedures to be performed at  
813 each visit, the number of visits, and what is expected of the patient, along with all  
814 possible side effects. A copy will be given to the subject and the original will be kept on  
815 file. Potential subjects may be screened for eligibility using a study-specific HIPAA  
816 waiver. Volunteers who call to inquire about the study will have their demographic and  
817 contact information collected over the phone, and the study will be described to them.

818 Once the subject has agreed to participate and appears in person, a study specific HIPAA  
819 Authorization will be signed, along with the consent form document.

820

821 Confidentiality/HIPAA:

822 Every effort will be made to keep all information about the patient confidential. Consent  
823 forms will be placed in the patient charts. Research records will be kept in a double-  
824 locked filing system in a secure locked room. The electronic study database will be  
825 encrypted and password protected and saved on the University's secure network. Only  
826 study personnel will have access to these records.

827

828 The institutional review board (IRB) governing this study may inspect the medical  
829 records of any patient involved in this study.

830

831 IRB Approval:

832 The study is approved by the UT Southwestern IRB.

833

834 FDA Approval:

835 An IND/NDA exception was granted by the FDA for possible use of rescue therapy with  
836 prandial insulin add-on to detemir-liraglutide combination should patients in the  
837 liraglutide arm reach the pre-defined failure end-point.

838

839 Declarations:

840 This study will be conducted in accordance with the Declaration of Helsinki.

841 This study will be conducted in accordance with the ICH GCP guidelines.

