#### 1075 **LIABILITY AND SUBJECT INSURANCE:**

1076 During and following a subject’s participation in trial, the sponsor-investigator and  
1077 his/her institution will provide adequate medical care to the study subject for any study-  
1078 related adverse events, including clinically significant laboratory values related to the  
1079 study. This medical care for study subjects will be provided regardless of their insurance  
1080 status.

1081

1082 The sponsor-investigator will be responsible for the conduct of the study and that the  
1083 sponsor-investigator agrees to defend, indemnify, and hold harmless Novo Nordisk, any  
1084 of its parent companies, affiliates, or subsidiaries, and their respective officers, directors,  
1085 employees, agents, representatives, distributors, salespersons, customers, licensees, and  
1086 end-users from and against any claim, suit, demand, loss, damage, expense or liability  
1087 imposed by any third party arising from or related to: (a) any breach of sponsor-  
1088 investigator's obligations; or (b) sponsor-investigator’s negligent or grossly negligent use  
1089 or willful misuse of the study drug, the results, or services derived therefrom. This  
1090 indemnification shall not apply in the event and to the extent that a court of competent  
1091 jurisdiction or a duly appointed arbiter determines that such losses or liability arose as a

1092 result of Novo Nordisk's gross negligence, intentional misconduct, or material breach of  
1093 its responsibilities.

1094

1095 **EVALUABILITY OF SUBJECTS:**

1096 All patients and collected data will be included in the intention to treat analysis.

1097 A secondary confirmatory analysis will be performed using only completers data, where  
1098 all data from patients with an overall compliance rate during the study period of <50%  
1099 will be excluded. The subjects and observations to be excluded, and the reasons for their  
1100 exclusion will be documented and signed by those responsible prior to database release.  
1101 The documentation must be stored together with the remaining trial documentation.

1102

1103 **PREMATURE TERMINATION OF STUDY:**

1104 Study can be discontinued if funding is withdrawn or by the Data Safety Monitoring  
1105 Board (DSMB) if there is evidence of futility or excess harm. The study statistician will  
1106 monitor the data quarterly and discuss any observed trends with the other members of the  

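### The ITT safety summary pools events after aspart rescue with events on liraglutide-detemir; one descriptive table split at visit 5 and at aspart start would separate them cheaply

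*Combined protocol and SAP*

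**What the plan says.** **Safety analysis.** The Statistical Analysis Plan says "Safety endpoints and hypoglycemic and other adverse events will summarize in detail" with descriptive statistics, and that "The analysis of safety data will be performed for the ITT" population. It describes the ITT set as "all randomized participants who receive at least one dose of a study medication"; Evaluability of Subjects adds that "All patients and collected data will be included in the intention to treat analysis". Neither wording stops or divides follow-up at rescue.

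**Rescue.** In the liraglutide arm the Rescue therapy section reads "hyperglycemia (defined as a confirmed Hb1c>10%) at the 3-mo visit (visit 5), meal-time" and, continuing, "insulin aspart will be initiated per the same protocol as above". The patient then completes the remaining visits to month 6. In the control arm the same HbA1c finding counts as treatment failure, but titration simply goes on and no drug is added.

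**What is to be compared.** The aim at the end of Background and Significance sets a GLP-1 plus basal regimen against basal-bolus, with hypoglycemia among the comparisons and superiority of the GLP-1 regimen hypothesized. Secondary outcomes 7 and 8 are episode counts and patients with any episode; 24 and 25 concern tolerability. Under FDA Approval, an exception was granted for "prandial insulin add-on to detemir-liraglutide combination should patients in the" liraglutide arm reach the failure endpoint.

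**The concern.** A rescued liraglutide-arm patient can spend up to three of six months on liraglutide, detemir and aspart, and aspart is the comparator arm's mealtime insulin. Hypoglycemic episodes and adverse events in that period enter the liraglutide arm's summary beside those on liraglutide-detemir. The change of regimen occurs in one arm only.

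Two things are then missing from the planned output. One is an estimate of hypoglycemia on the GLP-1 plus basal regimen itself, which is what the aim names. The other is any aggregate account, with a denominator, of safety on the combination covered by the FDA exception. The other analysis sets do not supply them: the per-protocol analysis, restricted to patients who stayed on their assigned intervention, is planned for HbA1c only, and the completers analysis excludes on compliance below 50%, not on rescue.

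**Working it through.** The plan gives no figure on this point to reproduce: no expected rescue proportion and no hypoglycemia rate. What follows is an illustration on assumed values.

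**Inputs from the documents.** 100 randomized 1:1, so 50 per arm (Sample Size Calculation, Randomization). Intervention 6 months (Study type). Rescue at month 3 with follow-up to month 6 (Rescue therapy), so a rescued patient spends about 3/6 = 0.5 of follow-up after rescue. Dropout is ignored, giving 50 x 0.5 = 25 person-years in the arm.

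**Assumed inputs.** f, the share of the arm rescued: 5%, 10%, 20%. R, the episode rate after rescue divided by the rate before: 2, 3, 5. Rescued patients are first given the arm's average rate before rescue, and the rate is otherwise taken as constant over time.

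**Exposure.** Person-time after rescue as a share of the arm's total is s = 0.5f:
- f = 5%: 2.5 patients, 0.625 person-years, s = 2.5%
- f = 10%: 5 patients, 1.25 person-years, s = 5%
- f = 20%: 10 patients, 2.5 person-years, s = 10%

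**Pooled rate relative to the pre-rescue rate:** I = 1 + 0.5f(R - 1). **Share of episodes arising after rescue:** 0.5fR / I.

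| f | R | I | Share after rescue |
|---|---|---|---|
| 5% | 2 | 1 + 0.025 x 1 = 1.025 | 0.05/1.025 = 4.9% |
| 10% | 3 | 1 + 0.05 x 2 = 1.10 | 0.15/1.10 = 13.6% |
| 20% | 5 | 1 + 0.10 x 4 = 1.40 | 0.50/1.40 = 35.7% |

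With f = 0 or R = 1 there is no inflation.

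**Sensitivity to the prior rate.** Rescued patients are those still above 10% HbA1c at month 3, so a lower prior hypoglycemia rate is plausible. Suppose it is half that of the other patients (assumed), with f = 20% and R = 5. The arm's pre-rescue rate is 0.8 x 1 + 0.2 x 0.5 = 0.9. Over six months it is 0.8 x 1 + 0.2 x (0.5 x 0.5 + 0.5 x 2.5) = 1.1. The ratio is 1.1/0.9 = 1.22, so 40% falls to 22%.

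**Precision on the combination.** With no events in n patients, the one-sided 95% upper limit is 1 - 0.05^(1/n): 45% for n = 5 and 26% for n = 10.

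**Can the data be split?** Assessments for Safety requires a date for each hypoglycemic episode, and adverse events are assessed at visits 2 to 6. But the minimum event fields under Adverse Events and Pregnancy contain no onset date. Rescue needs a confirmed HbA1c, so aspart may start after visit 5. The start-date requirement for concomitant medication excludes trial products, and aspart is one. The split is therefore available for hypoglycemia once the aspart start is known, but is not assured for other events.

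**The case against.** Analysis by randomized arm is a legitimate choice. The plan tests a liraglutide treatment strategy, rescue is a pre-specified step of it, and harm after rescue belongs to it. This stands, and the ITT summary should remain. If aspart raises the episode rate, the pooling also counts against liraglutide, so it does not flatter the hypothesis of superiority.

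A reader might infer that harm on the combination is never reported. The documents do not support that. All adverse events go to the DSMB at each meeting, SAEs go to the IRB and the drug supplier, and serious unexpected events go on the FDA form. Drug and causality are among the minimum fields for serious events. What is absent is a planned aggregate with a denominator.

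A reader might also infer that descriptive tables are the only look at hypoglycemia. Episodes and tolerability are also secondary outcomes, with logistic or mixed models planned for binary and continuous endpoints. These have no rule for time after rescue either, and no summary to visit 5 is named.

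Nor do the documents show that aspart adds risk. The Risks of Liraglutide text says the hypoglycemia risk "is higher if taking it with another medicine that can cause hypoglycemia, such as a sulfonylurea or insulin", but every liraglutide-arm patient takes detemir from the start, so it applies before rescue as well. The FDA exception, as described, carries no stated duty to report the combination separately.

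Finally, grouping by randomized arm is itself inferred: the plan names a population, not a grouping. It is the natural reading, since no other grouping is given. The small numbers on the combination are a fair limit on what a split can show.

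**Conclusion.** This is a cheap improvement, not an error in the safety analysis. The planned summary answers the strategy question. It does not isolate hypoglycemia on liraglutide-detemir, and it gives no aggregate view of the liraglutide-detemir-aspart combination. The size cannot be determined from the documents. The 2.5% to 40% range rests on 5-20% rescued, a rate ratio of 2 to 5, and an average prior rate in rescued patients; the upper end is a corner case and shrinks to 22% if their prior rate was half that of others. With no rescues there is no effect. The primary result and the sample size are untouched.

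**What to change.** Keep the ITT safety summary. Add one sentence to the Statistical Analysis Plan and one descriptive table:

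1. Hypoglycemia by severity, and adverse events, with person-time, in both arms from randomization to visit 5. No rescue can precede that visit, so this is an unmixed comparison of the randomized regimens.
2. For the liraglutide arm after visit 5, events and person-time shown separately for rescued and non-rescued patients, with every event after aspart start listed.

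Record the actual aspart start date and an onset date for each adverse event.

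The cost is one sentence, one table and two data fields. Few patients will be on the combination, so that part is description only, without testing. Comparisons after month 3 are not fully randomized, so they belong beside the ITT summary and do not replace it. No dose or rescue rule changes.
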